### **Specific project objectives:**

1. To design a prototype of the DSME intervention
2. To refine the intervention prototype and trial design
3. To evaluate the effectiveness and cost effectiveness of intervention under two alternative modes of delivery (nurse-led and peer-led)

4. To identify the most scalable model for DSME delivery in the Thai healthcare system

The primary hypothesis is that either model of DSME delivery will be effective and cost-effective; however, the peer-led model will be a more scalable option for the Thai healthcare system.

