#### 4.1.1 STUDY OUTCOME MEASURES

The study outcomes are:

- i. A difference in trial arms at one-year follow-up in HbA1c (co-primary outcome 1)
- ii. A difference in trial aims at one-year follow-up in total cardiovascular risk (co-primary outcome 2)

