## 5. RANDOMISATION

Twenty-one primary care units will be randomized (7 each) to provide nurse-led DSME, peer-led DSME, or standard care (1:1:1). Randomisation will be minimised by primary care networks to account for any variation in practice, although this is expected to be small because it is determined by the tertiary care hospital, which is same for both. The nurses and village health volunteers in intervention arms will be trained to deliver the intervention (at the community hospital or neighbourhoods as appropriate) using training films. No changes will be made to standard care, which currently involves a brief didactic educational session at the time of diagnosis of diabetes. While diabetes is diagnosed at tertiary hospitals, it is managed at, which are served by a full-time nurse (doctor visits weekly), and 10-15 village health volunteers linking patients in the community.

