### 9.1. SAMPLE SIZE CALCULATION

This study was powered to detect a clinically important difference of 0.6 units HbA1c (SD 1.5 units) between the control and intervention arms. We required 693 participants from 21 hospitals (7 per arm) to achieve 80% power at 2.5% significance level (to account for multiple testing), assuming an ICC between hospitals of 0.02 and loss to follow-up rate of 20%.

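### If the 2.5% planning level becomes a fixed test threshold, Holm's procedure on the same two HbA1c comparisons would do better at the same overall 5%

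*Combined protocol and SAP*

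**What the plan says.** Section 9.1 plans for a "clinically important difference of 0.6 units HbA1c (SD 1.5 units) between the control and intervention arms". The trial is sized "to achieve 80% power at 2.5% significance level (to account for multiple testing"). The other inputs are in the same section: "We required 693 participants from 21 hospitals (7 per arm"), "assuming an ICC between hospitals of 0.02 and loss to follow-up rate of 20"%. Section 5 allocates the units equally: they are "randomized (7 each) to provide nurse-led DSME, peer-led DSME, or standard care (1:1:1"), so both DSME arms are compared with one control arm.

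Section 3 gives the aim of the comparisons: "The primary hypothesis is that either model of DSME delivery will be effective and cost-effective". Section 4.1.1 lists two co-primary outcomes at one year, HbA1c and total cardiovascular risk.

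Section 10.2.1 specifies intention to treat and mixed-effects models. It gives no significance level, testing procedure or confidence level. The documents do not say which tests the 2.5% is shared between, whether it is two-sided, or what the overall error level is. They give no power for showing both models effective.

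**The concern.** The 2.5% in 9.1 is the only multiplicity control in the documents, so an analyst could well apply it as a fixed threshold to each comparison with control. That is Bonferroni for two tests. Holm's procedure tests the smaller p-value at 2.5% and, if it passes, the other at 5%. It holds the overall error at 5% under any dependence between the tests.

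The difference lies in the second comparison. Suppose nurse-led DSME has succeeded and peer-led DSME gives p = 0.03. The fixed rule calls peer-led negative; Holm calls it positive at the same overall level. If the primary hypothesis is read as a claim about both models, the relevant power is that of two rejections, which is lower than the 80% in 9.1.

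**Working it through.** **Inputs.** From 9.1: difference 0.6, SD 1.5, level 2.5%, power 80%, ICC 0.02, 7 clusters per arm, 20% loss, 693 recruited. From section 5: 1:1:1 allocation, so the two test statistics share a control arm and have correlation 0.5. Assumed: a two-sided level, a true difference of 0.6 in both arms, and a normal approximation unless stated.

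**Step 1: the plan's own figure.**
- Per arm before clustering: n = 2(2.2414 + 0.8416)² × (1.5/0.6)² = 118.8, rounded up to 119.
- Analysed per cluster with 7 clusters per arm: m = 119 × 0.98 / (7 − 119 × 0.02) = 25.2, rounded up to 26.
- Recruited per cluster: 26/0.8 = 32.5, rounded up to 33. Total: 33 × 21 = 693, as stated.
- A one-sided 2.5% gives 525 by the same route, so the two-sided reading is the one that fits.

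**Step 2: standard error with 693 recruited.**
- Analysed per cluster: 33 × 0.8 = 26.4.
- Variance of a cluster mean: 1.5² × (0.02 + 0.98/26.4) = 0.1285.
- SE of a contrast: √(2 × 0.1285/7) = 0.1916. Expected z: 0.6/0.1916 = 3.131.

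**Step 3: power.** Let J(a, b) be the bivariate normal probability, correlation 0.5, that one comparison passes level a and the other level b.
- One comparison at 2.5%: Φ(3.131 − 2.241) = 81.3%.
- Both, fixed rule: J(2.5%, 2.5%) = 70.5%.
- At least one, either rule: 2 × 81.3% − 70.5% = 92.1%.
- Both, Holm: 2 × J(2.5%, 5%) − J(2.5%, 2.5%) = 2 × 74.95% − 70.5% = 79.4%.
- Per comparison, Holm: (92.1% + 79.4%)/2 = 85.7%.

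| Two HbA1c comparisons | Fixed 2.5% | Holm, overall 5% |
|---|---|---|
| Per comparison | 81.3% | 85.7% |
| At least one | 92.1% | 92.1% |
| Both | 70.5% | 79.4% |
| Both, t on 18 df (simulated) | 63% | 74% |
| Weaker arm, true effects 0.6 and 0.45 (simulated) | 54.2% | 63.0% |

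With loss of 10% or 30% in place of 20%, the fixed-rule figure for both is 74.8% or 65.3%, against 82.9% or 74.9% with Holm.

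**Step 4: error, HbA1c pair only (simulated).**
- No effect in either arm: the chance of any rejection is about 4.7% under both rules.
- Effect of 0.6 in one arm and none in the other: the ineffective arm is falsely rejected in 2.5% of trials with the fixed rule and about 4.3% with Holm.

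**Step 5: error over both co-primary outcomes (simulated).** Two comparisons on two outcomes make four tests. The documents give no effect size or SD for cardiovascular risk, so the same standardised effect was assumed as for HbA1c. Let nurse-led work on both outcomes and peer-led on neither, with a between-outcome correlation from 0.8 to 0. The chance of a false peer-led claim on either outcome is then 4.0% to 4.9% with a fixed 2.5% on all four tests, and 6.7% to 8.3% with Holm applied separately within each outcome.

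**The case against.** **The plan does not adopt the rule criticised.** The 2.5% appears only as a level for sizing the trial. A reader might infer that the plan commits itself to fixed 2.5% tests and so throws power away. The documents do not support that: 10.2.1 is silent, and sizing at 2.5% is compatible with a step-down analysis. This stands, so the point is conditional on the level being carried over.

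**The family is not defined.** The 5% is inferred, and the 2.5% could be meant for the two comparisons or for the two outcomes. Holm dominates the fixed rule for either pair, but the 71% and 79% belong to the HbA1c comparisons. A reader might also infer that the fixed threshold buys no error control at all. Step 5 shows otherwise across four tests, and step 4 shows a lower false-rejection rate for a single ineffective arm. This stands.

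**Both successes may not be needed.** The wording "either model of DSME delivery will be effective and cost-effective" is ambiguous. If one success is enough, Holm adds nothing, and the final choice of model also rests on scalability, cost and acceptability. This stands as a limit on importance.

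**The size depends on the model.** Section 10.2.1 allows baseline adjustment. With an assumed baseline–outcome correlation of 0.3, 0.5 or 0.7, fixed-rule power for both is 76%, 86% or 97%, and the gain from Holm is about 8, 5 or 1.5 points. The gain shrinks but does not reverse.

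**Bonferroni is valid, and its intervals match its decisions.** That is true and is a fair reason to prefer it, but the loss of power should then be a stated choice.

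**Conclusion.** This is a cheap improvement. For the two HbA1c comparisons, a fixed 2.5% threshold is dominated by Holm at an overall 5%: about 9 points more power to show both models effective (71% to 79%; 63% to 74% with t on 18 df) and no change in the 92% for at least one. The figures rest on the inputs of 9.1, a true difference of 0.6 in both arms, a shared control, no baseline adjustment, and an overall 5% that the documents imply but do not state.

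A reader might infer from the 71% that the trial is undersized against its own target. It is not: 9.1 claims 80% per comparison, and 693 participants deliver it on the formula that reproduces that number.

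**What to change.** Keep 693 participants and 2.5% as the planning level. Add to 10.2.1:

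*The nurse-led versus control and peer-led versus control comparisons of 12-month HbA1c will be tested by Holm's procedure at an overall two-sided 5% level.*

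In the same edit, state how cardiovascular risk enters the family, by one of two routes:
- Holm over all four primary tests at 5%. The first step is then at 5%/4 = 1.25%, where one HbA1c comparison alone has power Φ(3.131 − 2.498) = 73.7%; later steps recover some of this.
- A statement that error is controlled at 5% within each outcome only, accepting the larger chance of a false claim across outcomes shown in step 5.

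In 9.1, report the power to show both models effective beside the per-comparison 80%.

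The cost is a few sentences, to be settled before outcome data are seen, with no extra participants. There are two downsides. If 97.5% simultaneous intervals are reported, they will not always match the second Holm decision, which needs a line of explanation. The false-rejection rate for an ineffective second arm rises from 2.5% to about 4.3%, still within the 5% for that pair.

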## STUDY SYNOPSIS

Type 2 diabetes is amongst the foremost challenges facing policy makers in Thailand, accounting for considerable death, disability and healthcare expenditure. Under Thailand's strong primary health system, medical management of diabetes is widely available. However, control of blood glucose and other cardiovascular disease risk factors, and regular screening for early detection of complications remain low due to a lack of services for education and counselling to support behavioural changes necessary for good self-management of the condition. A substantial literature documents the effectiveness of Diabetes Self-Management Education (DSME) programs for improving diabetes outcomes, although little high-quality data are available in Thailand, and traditional delivery models (health-professional led one-to-one or small-group sessions) are unlikely to be scalable in Thailand given current human resource and budgetary constraints. Thus, we propose to develop a low-cost DSME program and scalable delivery model for roll-out within the Thai primary care system.

The intervention is based on behaviour-change and social support theories. This will be delivered in monthly group meetings by lay health workers or nurses, and aided by a suite of short films to introduce key topics and stimulate discussion. We will randomise 21 primary care units to offer DSME to adults diagnosed newly diagnosed with type 2 diabetes and those with poor controlled type 2 diabetes diagnosed within the first three years. This will be delivered by lay health workers, nurses (for comparative effectiveness), or usual care. After 12 months, we will compare glycaemic control and cardiovascular risk scores between the three arms. We will conduct cost-effectiveness, process and policy evaluations to produce best-buy recommendations for the Thai Ministry of Public Health.

[figure not shown]
Through our 3-arm trial design, we will be able to compare effectiveness of nurse-, peer-delivered and standard care, and this along with the process evaluation will provide important lessons for the field of peer-delivery of interventions. In particular, questions remain whether peer educators can be easily trained to effectively deliver state-of-the-art behavioural counselling techniques based on a manualised intervention. The potential for peers to offer long-term support, which might better sustain behaviour change, is also untested and will be investigated through our process evaluation.

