## 10.2. DATA ANALYSIS

### 10.2.1 QUANTITATIVE ANALYSIS

Available outcome data will be analysed on an intention to treat basis. Potential clustering of outcomes at the level of community hospitals will be accounted for using mixed-effects models. Adjustment for baseline imbalances in outcomes or relevant covariates will be considered as appropriate. Effects of variations in intervention uptake and other relevant effect modifiers will be explored.

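### Is a 2.5% significance level too lenient for two co-primary outcomes and two intervention arms?

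*Combined protocol and SAP*

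**What the plan says.** Section 9.1 bases the sample size on HbA1c alone, for a "clinically important difference of 0.6 units HbA1c (SD 1.5 units) between the control and intervention arms". It asks for "80% power at 2.5% significance level (to account for multiple testing"), with 7 hospitals per arm, an ICC of 0.02 and 20% loss to follow-up, and arrives at 693 participants.

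Section 5 sets the arms: "Twenty-one primary care units will be randomized (7 each) to provide nurse-led DSME, peer-led DSME, or standard care (1:1:1"). Section 4.1.1 names two outcomes: "A difference in trial arms at one-year follow-up in HbA1c (co-primary outcome 1"), and a difference "at one-year follow-up in total cardiovascular risk (co-primary outcome 2"). The Study Synopsis describes the comparison broadly: "After 12 months, we will compare glycaemic control and cardiovascular risk scores between the three arms".

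Section 3 puts the primary hypothesis in terms of the two delivery models, expecting each to work, and adds a separate claim that the peer-led model scales better. Section 10.2.1 gives the analysis: intention to treat, and "Potential clustering of outcomes at the level of community hospitals will be accounted for using mixed-effects models". It gives no order of testing and no rule on whether one or both co-primary outcomes must be met. No section states an overall error level.

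**The concern.** A level of 2.5% is what results from halving 5%, so it looks like a correction for two tests. A count of outcomes times arms gives four comparisons with standard care. If any one of them could be declared a success, the correction would cover only half of them, and the chance of a false positive somewhere would exceed 5%. It also matters which result counts as the intervention having worked. A finding on cardiovascular risk alone, in one arm, could be presented as success or as failure. The trial is unblinded and is meant to inform national policy, so a reader would want that settled before results are seen.

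**Working it through.** **Inputs.** From section 9.1: difference 0.6, SD 1.5, power 80%, level 2.5%, ICC 0.02, 7 hospitals per arm, 20% loss. From sections 4.1.1 and 5: two outcomes and two comparisons with control. Assumed: an overall two-sided target of 5%; a correlation between outcomes of 0 to 0.8; large-sample tests.

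**1. Reproduce the plan's figure.**
- Per arm before clustering, at two-sided 2.5%: n = 2 × (2.2414 + 0.8416)² × 1.5² / 0.6² = 118.8.
- Per hospital with 7 hospitals per arm: 118.8 × (1 − 0.02) / (7 − 118.8 × 0.02) = 25.2, rounded up to 26.
- Allowing for loss: 26 / 0.8 = 32.5, rounded up to 33.
- Total: 21 × 33 = 693, as stated.

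The same steps at two-sided 5% give 98.1 per arm, 20 per hospital, 25 recruited and 525 in all. So the 2.5% is two-sided, and the correction really is built into the sample size.

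**2. Error if all four tests form one family and any one suffices.**
- Bonferroni bound: 4 × 2.5% = 10%.
- If the tests were independent: 1 − 0.975⁴ = 9.6%.
- With the shared control arm (simulation, no true effects, critical value 2.2414):

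| Outcome correlation | Four tests, familywise | One arm, its two outcomes |
|---|---|---|
| 0 | 9.1% | 4.9% |
| 0.5 | 8.5% | 4.6% |
| 0.7 | 7.9% | 4.3% |
| 0.8 | 7.4% | 4.0% |

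The four-test column includes errors in either direction. The chance of falsely claiming benefit over standard care is about half of it, 4.6% to 3.7%.

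**3. Error under the other readings.**
- *Both outcomes required in an arm.* An arm can be falsely declared successful only if a test of a true null hypothesis rejects in it. That leaves at most one critical 2.5% test per arm, so the bound is 2 × 2.5% = 5%. The worst case is a real effect on one outcome in one arm and on the other outcome in the other arm. At correlation 0 it gives 1 − 0.975² = 4.94%.
- *One three-arm test per outcome.* Two tests at 2.5%, bound 5%.
- *Each arm as its own question.* Two outcomes at 2.5%, bound 5%; simulated 4.9% to 4.0% (right-hand column above). Either outcome may count here.

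**4. Cost of correcting for four tests.**
- At two-sided 1.25% the steps in item 1 give 139.4 per arm, 32.4 rounded up to 33 per hospital, 33 / 0.8 = 41.25 rounded up to 42, and 21 × 42 = 882. That is 189 more than 693.
- If 693 is kept with 26 analysed per hospital: effective n per arm = 26 × 7 / (1 + 25 × 0.02) = 121.3; standard error = 1.5 × √(2 / 121.3) = 0.193; 0.6 / 0.193 = 3.12. Large-sample power is Φ(3.12 − 2.24) = 81% at 2.5% and Φ(3.12 − 2.50) = 73% at 1.25%.

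**The case for a change.** The strongest case for a change is that the omission is certain. Nothing in sections 4.1.1, 9.1 or 10.2.1 says how the second co-primary outcome enters the correction, and the readings lead to different claims of success. If the nurse-led versus peer-led comparison were also a primary test, there would be six tests, and the simulated error is 9.1% to 12.5% for correlations from 0.9 down to 0. A remedy with no extra participants exists: test HbA1c first in each arm at 2.5%, and cardiovascular risk there only if HbA1c succeeds. That keeps 693 and holds the error within 5%.

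The omission stands as a fact about the text. The rest carries less weight. Excess error needs three unstated conditions together: a 5% overall target, both arms pooled into one family, and success on either outcome. Section 9.1 speaks of control against the intervention arms on HbA1c, so its nearest reading is one test per arm, which 2.5% covers. Section 3, with its separate expectations for the two models, also fits treating each arm as its own question.

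The gated order is more than wording. It would stop cardiovascular risk from succeeding on its own, although section 4.1.1 makes it co-primary. The version proposed would also make nurse-led versus peer-led secondary, although the Study Synopsis includes nurses for comparative effectiveness. Those are decisions about the trial's aims, on which statisticians could reasonably differ.

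One limit remains: if both outcomes are required, the 80% in section 9.1 is the power for HbA1c and not for joint success. The protocol gives no effect size or SD for cardiovascular risk, so any joint figure would rest on invented inputs.

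**Conclusion.** The concern does not require a change. The stated level, power and sample size agree with one another. The 2.5% is adequate under three ordinary readings, each at or below 5%, and falls short only under a fourth, where the error would be 7.4% to 9.1%. That range assumes a 5% two-sided target, outcome correlations of 0.8 down to 0, and large-sample tests; the protocol states none of these. The gap is one that the trial statistician can fill sensibly when specifying the detailed analysis, by choosing one reading before the arms are compared. Readers can also judge each of the four comparisons with standard care against 2.5%. Imposing a particular rule now would cost either the standing of a co-primary outcome or 189 more participants, to cure an excess that the text does not establish.

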### 9.2. FORMAT AND SCALE OF THE DATA

Data will be collected from approximately 693 individuals newly diagnosed with diabetes, across 21 primary care units in the Chiang Mai and Lampang province of Thailand.

The following data will be collected at baseline, 6 months and 12 months:

- a. Questionnaire and body measurement data will be collected in person and entered where possible directly into a password-protected Microsoft Access database (via a form) on laptops, or else using double-entered paper forms.
- b. Blood samples will be labelled and sent for analysis at the local hospital lab, and once analysed the results will be merged back into the main database. Once fully entered and validated, data will be transferred to comma separated value (csv) files for more efficient long-term storage and sharing
- c. Qualitative data will be collected via interview and direct observation, and initially stored as voice and video recordings, later transcribed and data extracted using NVivo software.

## 10. DATA QUALITY AND STANDARDS

A data collection protocol will be developed, and the project coordinator in Thailand will provide training to fieldworkers before data collection commences. Validation will be performed on a Data Management on a random sample of questionnaire data by cross-checking with clinic records. Any discrepancies will be followed-up and addressed by field workers, re-contacting participants to clarify as necessary. Quantitative data will be entered directly via a form with built in data checks to minimise transcription errors (or where necessary collected on paper and later double-entered into the electronic form). Post entry checks will be conducted using statistical software. Blood samples will be collected by trained phlebotomists in NaF vacutainers for blood glucose estimation; stored in ice slurry and centrifuged and separated after 30 minutes of collection to prevent glycolysis, and the plasma will be dispensed to the lab for analysis. All hospital laboratories have their own internal quality assurance protocols and are also linked to a national external quality assurance mechanism. Fieldworkers will be trained in qualitative methods and an interview schedule will be devised. Project coordinators will spot-check interview transcripts to ensure quality.

### 10.1. DATA MANAGEMENT

Data will be uploaded to a secure server at Chiang Mai University as soon as possible. Copies of data with numerical study identifiers replacing other identifying information will be transferred to LSHTM for analysis using a secure encrypted data transfer service (MyFiles, previously Filr). Interviews will be recorded on digital Dictaphones and immediately transferred to a secure local server at CMU on completion. Following transcription, data will be transferred to LSHTM as above. Audio recordings will be kept until transcription has been completed and verified, after which they will be deleted. LSHTM data systems are maintained in accordance with LSHTM's Information Management & Security Policy, backed-up and virus scanned on a daily basis. All staff involved in research will be trained in the study procedures and data management before the study commences.

